5.1.1.3 TTF

Time to treatment failure is defined as the time (in months) from the date of randomization until the date of the last study treatment. Subjects who are still on study treatment as of the cutoff date will be censored at the date of the last study treatment or the cutoff date, whichever comes first. A list of the definition of TTF events is presented in Table 5-3.

Table 5-3 Definition of TTF events

	Case	Date
Event	Discontinued study treatment	Date of the last study treatment
Censoring	Other cases	Date of data cutoff

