10.1.2 Administration schedule

The administration schedule for each treatment group is shown below. The administration period is until 31 Jan 2020.

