13.1 Discontinuation criteria for individual subject

13.1.1 Study Treatment Discontinuation Criteria

Discontinue the study treatment if any of the following occur:

- Disease progression defined by RECIST version 1.1
- Patient has an adverse event (AE) that in the opinion of the investigator (subinvestigator) requires the study treatment to be discontinued
- Patient has not taken the study drug for more than 28 consecutive days
- Application for curative surgery due to tumor shrinkage
- Patient has a critical protocol deviation
- Pregnancy
- Patient request to discontinue the study treatment
- The investigator (subinvestigator) concludes that the patient needs to discontinue the study treatment
- Study is completed

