14.5 Time to Treatment Failure (TTF)

Time to treatment failure is defined as the time from the date of randomization until the date of last dose of study treatment. Patients who are still on study treatment as of the cut-off date will be censored at the last date of study treatment, or the cut-off date, whichever is earlier.

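### SAP Table 5-3 censors TTF on a different date from the SAP text and protocol 14.5, and at the final evaluation it scores study completion and the administrative end of dosing as treatment failure

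*SAP*

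**What the plan says.** **Definition.** Both documents run TTF from randomisation to the last dose. The SAP (5.1.1.3) has "Time to treatment failure is defined as the time (in months) from the date of randomization until the date of the last study treatment"; protocol 14.5 has "until the date of last dose of study treatment".

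**Event.** Table 5-3 has one event row, "Discontinued study treatment", dated at the last study treatment. No discontinuation reason is excepted.

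**Censoring.** The SAP text says that patients still on treatment at cutoff are "censored at the date of the last study treatment or the cutoff date, whichever comes first". Protocol 14.5 gives the same rule. The censoring row of Table 5-3, which covers everyone without an event, gives "Date of data cutoff".

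**Reasons for stopping.** Protocol 13.1.1 lists "Application for curative surgery due to tumor shrinkage" and "Study is completed" among the treatment discontinuation criteria. Protocol 10.1.2 adds: "The administration period is until 31 Jan 2020".

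**Use.** TTF is a named secondary endpoint, analysed in the same manner as OS apart from a few exclusions (SAP 7.1.3), hence with log-rank tests and hazard ratios. SAP 1.1 covers both the primary and the final evaluation.

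**The concern.** Two programmers working from SAP 5.1.1.3, one from the sentence and one from the table, would build different TTF datasets. The table is the outlier, since the protocol sides with the sentence.

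The table's date also sits badly with the way events are dated. A patient in a rest period at cutoff who never takes another dose has a TTF ending at the last dose, before the cutoff. Censoring at cutoff treats that patient as known to be failure-free for longer than the endpoint allows. Censoring at last treatment does not.

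The second problem is one of meaning. A patient still benefiting when the sponsor closes dosing has not failed treatment, yet falls under the only event row. If one arm keeps patients on treatment longer, that arm collects more of these artificial failures in the final TTF comparison.

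**Working it through.** The documents give no event count or power for TTF, so there is no TTF figure to reproduce. As a check on the design model used in step 3, the OS event formula in SAP 2.1.2 gives 4 × (1.9687 + 1.0364)² / (ln 0.75)² = 4 × 9.031 / 0.08276 = 436.5, that is, the stated 437.

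**1. Gap between the two censoring dates**

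| Patient at cutoff | Last oral dose | Cutoff falls on | Gap (table minus text) |
|---|---|---|---|
| Arm A, scheduled rest (protocol 10.1.2.1) | Day 7 | Day 8–14 | 1–7 days |
| Arm B, scheduled rest (10.1.2.2, 10.1.2.3) | Day 21 | Day 22–35 | 1–14 days |
| Either arm, interrupted | – | before the rule of more than 28 days off drug applies (13.1.1) | up to 28 days |

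At 30.4375 days per month, 7, 14 and 28 days are 0.23, 0.46 and 0.92 month.

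**2. Which stops become events.** Protocol 16.1.3 places the final evaluation at the end of the trial, on all data gathered. The study period runs to May 2020 (protocol 25), after dosing closes on 31 Jan 2020. Patients stopped by that date are then no longer on treatment, so the censoring sentence does not cover them and the event row does.

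**3. Is the primary evaluation affected?** Inputs: 650 FAS patients, uniform accrual over 19 months, MST 14.5 and 19.33 months, exponential survival. Expected deaths at month T are

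D(T) = Σ 325 × [1 − (e^(−λ(T−19)) − e^(−λT)) / (19λ)], with λ = ln 2 / MST.

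- D = 491 at T = 44.3 (about 261 deaths in Arm B and 230 in Arm A).
- With assumed longer MSTs of 19 and 25 months, T = 54.4.
- SAP Table 4-1 dates 219 deaths at 30 Nov 2016, about month 24, when the plan would expect D(24) = 285. If the whole shortfall is longer survival (both MSTs × 1.42), T = 58.6. If it is a 4-month later start, T = 48.3.

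Counting from 1 Dec 2014, 31 Jan 2020 is month 62. In every case the primary cutoff comes first, and patients then on treatment are censored.

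**4. How many are still dosed on 31 Jan 2020?** No TTF figure is given, so phase II PFS (protocol 2.4) is the proxy: 8.3 months for Arm A, 5.6 for Arm B, exponential, 343 per arm. The share still treated at month 62 is (e^(−43λ) − e^(−62λ)) / (19λ).

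- Arm A: λ = 0.0835; (0.0276 − 0.0056) / 1.587 = 1.4%, or 4.7 patients.
- Arm B: λ = 0.1238; (0.00488 − 0.00046) / 2.352 = 0.19%, or 0.6 patients.

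The total is about 5.

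**5. Does last-dose dating favour an arm?** Assume dosing on schedule from the day of randomisation, with progression found on the nominal 6-weekly scan before that day's dose.

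| Scan day | Last dose, Arm A | Last dose, Arm B | A − B (days) |
|---|---|---|---|
| 43 | 35 | 42 | −7 |
| 85 | 77 | 84 | −7 |
| 127 | 119 | 126 | −7 |
| 169 | 161 | 161 | 0 |
| 211 | 203 | 196 | +7 |

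If treatment starts 8 days after randomisation, the first-scan gap is +13 days (Day 42 against Day 29). It is then zero at Days 85, 127 and 169. The sign depends on start day and scan.

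**The case against.** The strongest reply is that any-reason discontinuation, dated at the last dose, is the prespecified endpoint in both documents. Reasons for stopping are tabulated by arm (SAP 7.6.3) and surgery by intent (SAP 7.8, Table 7-3), so a reader can see what lies behind the events. The administrative stop touches a handful of patients, and only at the final evaluation. All of this stands, and it limits the point. It does not reconcile the table with the text.

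It might also be said that SAP Table 7-2 equates last treatment with cutoff for ongoing patients. SAP 7.6.7 sets that rule out for the outpatient-visit calculation, so it does not govern TTF.

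A reader might infer two stronger criticisms.

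- **That last-dose dating biases the arm comparison because the cycles differ.** The enumeration above shows gaps of both signs and of zero, so no stable direction can be claimed. A switch to a decision date is not supported either. Protocol Table 11.1-1 lists no such date, and in an open-label trial the last dose is the more objective one.
- **That curative surgery after shrinkage should be censored in the main definition.** Phase II response rates of 66% and 46% (protocol 2.4) make it plausible that such surgery is commoner in Arm A, but the documents give no surgery rate. If 5% and 2% of discontinuations were surgical, the hazard ratio would move by about 0.98/0.95 = 1.03 against Arm A; at 10% and 2%, by 0.98/0.90 = 1.09. Those shares are assumptions. Censoring selected responders on an investigator's decision may itself be informative. This is a trade-off that belongs in a sensitivity analysis.

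**Conclusion.** Two points hold on the text. Table 5-3 contradicts SAP 5.1.1.3 and protocol 14.5 on the censoring date, by up to 7 days in Arm A and 14 days in Arm B during scheduled rest, and by up to 28 days in an interruption. And its unqualified event row turns study completion and the 31 Jan 2020 end of dosing into treatment failures at the final evaluation.

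The second effect is small: roughly 5 patients, mostly in Arm A, assuming exponential time on treatment with phase II PFS as the proxy and recruitment as planned. The primary evaluation is expected to be unaffected, because the 491st death is projected at about months 44 to 59 against month 62. The documents do not support changing the date of the event or the main any-reason definition. TTF is secondary, with no stated power, and the OS conclusion stands apart from it.

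**What to change.** 1. Change the censoring row of Table 5-3 to the rule already in the text, "censored at the date of the last study treatment or the cutoff date, whichever comes first". It then agrees with SAP 5.1.1.3, protocol 14.5 and the last-dose dating of events.
2. In SAP 5.1.1.3, Table 5-3 and protocol 14.5, state that patients who stop solely because the study is completed, or because the administration period ends on 31 Jan 2020, are censored at their last study treatment.
3. Keep any-reason discontinuation dated at last dose as the main TTF analysis. Add one sensitivity analysis that censors patients who stop for curative surgery due to tumour shrinkage, and report their number by arm.

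The cost is wording in both documents, one adjusted derivation from discontinuation reasons that are already tabulated, one extra analysis, and a few fewer TTF events at the final evaluation.

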5.1.1.4 Best Overall Response Assessment

Best overall response as per RECIST version 1.1 is the best response recorded from the start of the study treatment until the end of tumor follow-up period. The confirmation of tumor response for CR or PR is not required, but if SD (or non-CR/non-PD) is confirmed as the best overall response, the criteria for SD (or non-CR/non-PD) must be met in a test conducted at least 6 weeks after entry (acceptable within 1 week before and after the scheduled date).

5.1.1.4.1 ORR

Overall response rate is defined as the proportion of subjects with the best overall response of CR or PR in the tumor response-evaluable population.

$$\text{ORR (\%)}: (\text{CR} + \text{PR}) / (\text{Number of subjects in the tumor response-evaluable population}) \times 100$$

5.1.1.4.2 DCR

The assessment of DCR will be parallel that of ORR, with DCR defined as the proportion of subjects with objective evidence of CR, PR, or SD.

$$\text{DCR (\%)}: (\text{CR} + \text{PR} + \text{SD}) / (\text{Number of subjects in the tumor response-evaluable population}) \times 100$$

5.1.1.4.3 Time to Overall Response

Time to overall response is defined as the time (days) from the date of study drug administration to the first overall response of CR or PR. The time to overall response will not be calculated if CR or PR is not evident.

$$\text{Time to overall response: Date of first overall response of CR or PR} - \text{Date of study drug administration} + 1$$

5.1.1.4.4 Time to Complete Response

Time to complete response is defined as the time (days) from the date of study drug administration to the first overall response of CR. The time to complete response will not be calculated if CR is not evident.

$$\text{Time to complete response: Date of first overall response of CR} - \text{Date of study drug administration} + 1$$

5.1.1.4.5 Tumor Shrinkage Rate

The sum of the longest diameters of target lesions at the time of imaging assessment $l = 0, 1, \dots, L$ ($l = 0$ at predose, $l \geq 1$ after the first dose and on and before the start date of subsequent therapy) is defined as R_l . Tumor shrinkage rate at the time of imaging assessment l in each subject is defined by the following expression:

$$\frac{100(R_l - R_0)}{R_0}$$

Maximum tumor shrinkage rate in each subject is defined by the following expression:

$$\text{Min}_{1 \leq l \leq L} \left(\frac{100(R_l - R_0)}{R_0} \right)$$

5.1.2. Safety Endpoints

5.1.2.1 Adverse Events and Adverse Drug Reactions

An adverse event (AE) is any untoward medical condition sign, symptom, or disease that occurs in a subject while participating in this study and does not necessarily have a causal relationship with the study drug.

Treatment-emergent adverse events are AEs that occur from the initiation of any study medication administration and do not necessarily have a causal relationship with the study drug.

Any untoward medical sign, symptom, or disease that occurs outside the period of safety follow-up (30 days after the last dose of study medication or until the start of new antitumor therapy, whichever comes first) is not considered an AE. If any AEs are observed after the safety follow-up period has ended, only those AEs suspected to have a causal relationship with the study drug will be recorded in the CRF.

The analysis of AEs will be based on treatment-emergent adverse events.

Adverse drug reactions in this study are defined as adverse events (including laboratory abnormalities) determined to have a reasonable possibility of a causal relationship with the study drug.

5.1.3. Compliance Endpoints

5.1.3.1 Total Dose

The dose in each cycle $l = 1, 2, \dots, L$ (the cycle of the last study treatment $l = L$) is defined as d_l . The definition of d_l in each arm is presented below.

A (TAS-118)

The d_l in Arm A (TAS-118) is defined by the following formula, where the number of doses of 30, 40, 50, and 60 mg is n_1, n_2, n_3 and n_4 , respectively:

$$d_l = 30n_1 + 40n_2 + 50n_3 + 60n_4$$

If an unspecified dose is administered, the d_l in Arm A (TAS-118) is defined by the following formula, where the dose is A and the number of doses is m :

$$d_l = 30n_1 + 40n_2 + 50n_3 + 60n_4 + \sum A_i m_i$$

A (L-OHP)

The d_l in Arm A (L-OHP) is defined as the actual dose [mg/body] administered in each cycle.

B (S-1)

The d_l in Arm B (S-1) is defined by the following formula, where the number of doses of 40, 50, and 60 mg is n_1, n_2 , and n_3 , respectively:

$$d_l = 40n_1 + 50n_2 + 60n_3$$

If an unspecified dose is administered, the d_l in Arm B (S-1) is defined by the following formula, where the dose is A and the number of doses is m :

$$d_l = 40n_1 + 50n_2 + 60n_3 + \sum A_i m_i$$

B (CDDP)

The d_l in Arm B (CDDP) is defined as the actual dose [mg/body] administered in each cycle.

The total dose is the sum of doses administered from the start of Cycle 1 study treatment through the discontinuation of study treatment and is defined by the following formula:

$$D = \sum_{l=1}^L d_l$$

5.1.3.2 Dose Intensity

The definition of actual dose intensity and relative dose intensity is presented in Tables 5-4 and 5-5, respectively.

Table 5-4 Definition of actual dose intensity

Arm		Definition	Unit
A	TAS-118	(Total dose [mg] / BSA [m ²] at entry) / ((Start date of the last cycle treatment – Start date of Cycle 1 treatment + 14) / 7)	[mg/m ² /week]
	L-OHP	(Total dose [mg] / BSA [m ²] at entry) / ((Start date of the last cycle treatment – Start date of Cycle 1 treatment + 14) / 7)	
B	S-1	(Total dose [mg] / BSA [m ²] at entry) / ((Start date of the last cycle treatment – Start date of Cycle 1 treatment + 35) / 7)	
	CDDP	(Total dose [mg] / BSA [m ²] at entry) / ((Start date of the last cycle treatment – Start date of Cycle 1 treatment + 35) / 7)	

Table 5-5 Definition of relative dose intensity

Arm		Definition	Unit
A	TAS-118	$100 \times \text{Actual dose intensity [mg/m}^2\text{/week]} / ((\text{Initial dose [mg]} \times 2 \times 7 / \text{BSA [m}^2\text{] at entry}) / 2 \text{ [week]})$	[%]
	L-OHP	$100 \times \text{Actual dose intensity [mg/m}^2\text{/week]} / ((\text{Initial dose [mg/body]} / \text{BSA [m}^2\text{] at entry}) / 2 \text{ [week]})$	
B	S-1	$100 \times \text{Actual dose intensity} / ((\text{Initial dose [mg]} \times 2 \times 21 / \text{BSA [m}^2\text{] at entry}) / 5 \text{ [week]})$	
	CDDP	$100 \times \text{Actual dose intensity [mg/m}^2\text{/week]} / ((\text{Initial dose [mg/body]} / \text{BSA [m}^2\text{] at entry}) / 5 \text{ [week]})$	

5.2. Common Considerations for Statistical Analysis

5.2.1. Data Handling

5.2.1.1 Handling of Longitudinal Data

5.2.1.1.1 Calculation of Number of Days and Period

In this statistical analysis plan, the number of days and period will be consistently calculated using the following formulas unless otherwise specified:

- After the reference date Day n = target date – reference date + 1
- Before the reference date Day n = target date – reference date

Accordingly, the start date of treatment is Day 1, the day following the start of treatment is Day 2, and the day before the start of treatment is Day –1. The period is 1 day when the target date is just the reference date and 2 days when the target date is the date following the reference date.

If the month is missing in a date used for the calculation, the number of days and period is regarded as missing. If only the day is missing, it is replaced with the first day before calculation (e.g., April xx, 2016 → April 1, 2016). Only when the date of death is missing (year and month observed) and the date of the last survival confirmation in the same year and month is known, the date of death is regarded as the date following the last survival confirmation.

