11.8 Survival Follow-up

All treated patients will be followed for survival status (alive/dead) and new anti-tumor therapy at scheduled 12-week (+/- 2 weeks) time intervals from randomization until death, and at the cutoff date for second interim analysis and primary evaluation. Patients will be followed until the target number of events (deaths) is met. The investigator (subinvestigator) should make every effort to contact the patient or primary caregiver to determine his/her survival status. Survival information must be documented in the patient's records. If patient wishes to discontinue the study treatment (including withdrawal of consent), survival follow-up will be continued.

12. Pharmacokinetics and Pharmacogenomics

Not included in this study.

13. Discontinuation of study

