5.1.1. Efficacy Endpoints

The efficacy endpoints in this study are the primary endpoint of OS and the secondary endpoints of PFS, TTF, ORR, and DCR, as well as the duration of overall response, the duration of complete response, and tumor shrinkage rate.

5.1.1.1 OS

Overall survival is defined as the time (in months) from the date of randomization to the date of death due to any cause. In the primary analysis, subjects who are not known to be dead or are alive as of the cutoff date will be censored at the date of the last survival confirmation or the cutoff date, whichever comes first.

The OS cutoff date used for the analysis is defined as the event date in the 491st subject in the FAS population. In the analyses in the enrolled population, the cutoff date is defined as the event date in the 491st subject in the enrolled population.

A list of the definition of OS events is presented in Table 5-1.

Table 5-1 Definition of OS events

	Case	Date
Event	Subjects died before the cutoff date.	Date of death
Censoring	Subjects failed to be followed up for death or are alive as of the cutoff date.	Date of the last survival confirmation* ¹ or the cutoff date, whichever comes first

*1: The latest date among the dates recorded in all pages of the CRF

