5.1.1.2 PFS

Progression-free survival is defined as the time (in months) from the date of randomization until the date of the investigator-assessed disease progression or death due to any cause, whichever comes first. Subjects who start to receive subsequent therapy before disease progression assessment will be censored at the date of the last progression-free assessment before subsequent therapy is initiated. A list of the definition of PFS events is presented in Table 5-2.

Subjects who are progression-free and alive as of the cutoff date will be censored at the date of the last progression-free assessment.

Table 5-2 Definition of PFS events

	Case	Date (if multiple cases apply, the earliest date is used)
Event	Progressive disease (PD) before the data cutoff date	Date of PD confirmation
	Death (PD not observed)	Date of death ^{*1}
Censoring	Non-PD or non-death at the time of data cutoff	Date of the last tumor assessment
	Unknown date of PD	Date of the last tumor assessment
	No tumor assessment after randomization	Date of randomization
	Another subsequent therapy for any reason other than PD	Date of the last tumor assessment before the start of subsequent therapy
	Evaluated as not evaluable (NE)	Date of the last tumor assessment immediately before evaluation
	Other	Date of the last tumor assessment

*1: If no tumor is assessed on the date of imaging assessment specified after the date of the last study treatment and a death event occurs before the acceptable limit of the imaging assessment day (the specified assessment day + 1 week), the event will be handled as a PFS event. If a death event occurs after the acceptable limit, the event is not handled as a PFS event.

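### A missing day is set to the 1st of the month with no floor at first dose, last study dose or progression, so a replaced date can reverse the true order of events

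*SAP*

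**What the plan says.** SAP 5.2.1.1.1 holds the only rule for partial dates:

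- Month missing: "If the month is missing in a date used for the calculation, the number of days and period is regarded as missing".
- Day missing: "If only the day is missing, it is replaced with the first day before calculation".
- Death: the exception begins "Only when the date of death is missing (year and month observed) and the date of the last survival confirmation in the same year"; the confirmation must fall in the same month as well. The death is then placed on the day after that confirmation. The footnote to Table 5-1 (SAP 5.1.1.1) defines the last survival confirmation as "The latest date among the dates recorded in all pages of the CRF".

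The places where a replaced date would be used are these:

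- **PFS text, SAP 5.1.1.2:** "Subjects who start to receive subsequent therapy before disease progression assessment will be censored at the date of the last progression-free assessment" preceding that therapy. This is a test of date order.
- **PFS table, SAP Table 5-2:** the censoring row reads "Another subsequent therapy for any reason other than PD". This is a test of reason. The table's date column takes the earliest date when several cases apply. Protocol 14.4 has the same pair of wordings.
- **Adverse events, SAP 5.1.2.1:** "Treatment-emergent adverse events are AEs that occur from the initiation of any study medication administration", and the analysis is confined to these events.
- **Clinical findings, SAP 7.10:** days from the start of Cycle 1 to first onset are summarised.

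SAP 5.2.1.2 separately states that missing data are not imputed.

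**The concern.** The 1st is the earliest day a partial date can take, so the replacement can only move a date backwards. For an adverse event onset or a new therapy start, backwards is the direction that crosses a boundary. The death exception protects one type of date from falling before known information; no equivalent exists for these two.

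Two consequences follow.

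- **(a) Adverse events.** An event that began after dosing, in the month of first dose, can be dated before first dose. Time to onset becomes negative. If the same date sets treatment-emergent status, the event leaves the adverse event tables.
- **(b) PFS.** Therapy begun after a progression in the same month can be dated before it. On the date-order text, a progression event is then replaced by censoring at the preceding scan. That censoring is informative, because the patient has in fact progressed.

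A therapy start placed too early also closes the adverse event window (SAP 5.1.2.1) and the last-cycle data window (SAP 5.2.1.1.3) too soon.

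**Working it through.** The plan gives no figure on this point to reproduce. The check applies the rule to examples and then to the calendar.

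**Inputs.** The day-1 rule and day-count formulas come from SAP 5.2.1.1.1. The mean month length L = 30.4375 days comes from SAP 5.2.1.1.2. Scans are every 6 weeks, within 1 week either side (Protocol 11.4). Survival contact is "at scheduled 12-week (+/- 2 weeks) time intervals from randomization until death" (Protocol 11.8). The gaps between events are assumptions.

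**Example for PFS.** Progression is on 15 April 2016 and therapy truly starts on 25 April, recorded without a day. The rule gives 1 April, which is before 15 April. On the date-order text the event on 15 April becomes censoring at the previous scan, about 42 days earlier, around 4 March.

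**Example for onset.** First dose is on 15 April and onset is truly on 22 April, recorded without a day. True Day = 22 − 15 + 1 = 8. The rule gives 1 April, and the formula for dates before the reference gives 1 − 15 = −14.

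**How often the order reverses, given a missing day.** Let progression fall on day d of a month and therapy g days later. The order reverses when both dates are in the same month and d is not the 1st. That leaves L − g − 1 days out of L, so the share is 1 − (g + 1)/L.

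- g = 7: 1 − 8/30.4375 = 0.737
- g = 14: 1 − 15/30.4375 = 0.507
- g = 21: 1 − 22/30.4375 = 0.277

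A count over every calendar day from December 2014 to May 2020 gives the same three values. The same shares apply to an adverse event that truly began 7, 14 or 21 days after first dose. For a true onset on the dosing day the share is 1 − 1/30.4375 = 0.967.

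**Which PFS wording decides.** The text works by date order and the table row by reason. The post-treatment items listed in Protocol Table 11.1-1 are whether it was given, the regimen, and the start and end dates. No reason is listed, so a program working from those items would have to use date order.

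**Partial death dates outside the exception.** Assume last contact is uniform over the G days before death. For G up to 28, the share with no confirmation in the same month is (G + 1)/(2L), and the mean backward shift among them is (G − 1)/3 days.

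- G = 14: 15/60.875 = 0.246; shift 13/3 = 4.3 days
- G = 28: 29/60.875 = 0.476; shift 27/3 = 9.0 days
- G = 84 (the 12-week schedule), by calendar count: 0.825; shift 13.6 days

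These deaths cannot fall before the last confirmation, because that lies in an earlier month. They move earlier, but no order is reversed.

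**The case against.** **Table 5-2 censors by reason.** Therapy prompted by progression is not therapy given for another reason, so on the table row the event stands whatever day is recorded. Reasons for discontinuing are source data (Protocol 19.1) and are tabulated (SAP 7.6.3), so the trigger can often be traced. This stands in part: loss of the PFS event is one reading of two conflicting wordings, not a settled outcome. It does not remove the problem, because the text carries no such limit.

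**The rule is written for durations.** It sits under the calculation of days and periods. The SAP does not say that a replaced date sets the treatment-emergent flag, and SAP 5.2.1.2 says missing data are not imputed. This also stands: use of the rule for the flag is an inference. It is a reasonable one, because adverse events are collected from consent (Protocol 15.1.1), a cut at first dose is needed, and no other partial-date rule exists. The onset calculation in SAP 7.10 needs no such inference.

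**Safeguards.** Onset dates must be documented (Protocol 15.1.1), data queries must be answered (Protocol 17.1), and an adverse event listing covers the enrolled population (SAP 7.2.1). These should reduce the number of partial dates and keep events visible. They do not correct the summary tables.

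**Stronger readings.** A reader might infer that every first-month onset with a missing day is misclassified. Collection starts at consent, so some of those events truly preceded dosing and are placed correctly. A reader might also multiply the shares above by an assumed number of progressors to obtain a count of lost events. The documents give neither that number nor the frequency of partial dates.

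**Conclusion.** The point holds as a gap in a stated rule, of minor to moderate weight. Followed as written, the rule can give a negative time to onset. If it also governs the flag, it can remove an event that began after dosing from the treatment-emergent tables. On the date-order text it can turn a PFS event into censoring about 6 weeks earlier.

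The 74%, 51% and 28% are conditional on a missing therapy day and on assumed gaps of 7, 14 and 21 days. They are not rates in the trial. No effect on the PFS hazard ratio, on adverse event rates or on the difference between arms can be derived from the documents. PFS is a secondary endpoint.

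Two readings about death should be avoided. One is that death dates are exempt: they are exempt only with a confirmation in the same month. The other is that overall survival is therefore biased. The shift is backward within the month, it applies by the same rule in both arms, and nothing in the documents suggests that partial death dates are common or unequal between arms.

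**What to change.** Add to SAP 5.2.1.1.1:

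- **Adverse event onset, day missing.** If the onset month is the first-dose month, use the first-dose date unless a recorded stop date or other data show an earlier onset. Otherwise use the 1st.
- **Subsequent therapy start, day missing.** Use the latest of the 1st, the day after the last study dose, and a documented progression date in the same month. Cap the result at the end of the month, and let data showing an earlier start override it.
- **Scope.** State that these rules also govern event ordering and flags, as an exception to SAP 5.2.1.2.

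In SAP 5.1.1.2, align the text with Table 5-2 so that one test decides whether new therapy censors. State that therapy dated on the day of progression does not precede it.

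The cost is a few sentences and a few lines of code, and SAP Section 8 provides for revision with reasons. There are two downsides. A few events that began before dosing may be counted as treatment-emergent, which is conservative for safety. A few therapies that truly began before progression may be treated as starting at progression; a sensitivity analysis of PFS using the 1st would show whether this matters.
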